6.2. Pre-treatment Assessments

6.2.1. Screening Visit

Subjects will be screened within 30 days before assignment to determine eligibility for participation in the study. The following will be performed and documented at screening:

- 1) Obtain written informed consent
- 2) Obtain medical history
- 3) Complete physical examination including, vital signs, body weight, and height

- 4) Screen for pregnancy (serum screen) and contraceptive use
- 5) Conduct preliminary liver chemistry tests (ALT, ALP, AST, total and direct bilirubin, total protein, albumin, GGT, LDH, CK), serum renal chemistry (glucose, creatinine, creatinine clearance (calculated), magnesium, bicarbonate, chloride, potassium, sodium) and urinalysis (glucose, protein, creatinine, phosphate, bicarbonate, blood, calcium) (to be averaged with Baseline renal chemistry values), fasting required
- 6) HBV serology (HBeAg and HBsAg; anti-HBe and anti-HBs (if Ag negative))

Subjects meeting all of the inclusion criteria and none of the exclusion criteria will return to the clinic within 30 days after screening for commencement into the study.

From the time of obtaining informed consent through the first administration of Tenofovir DF, record all renal and bone AEs and any SAEs (not limited to bone or renal) on the adverse events case report form (CRF/eCRF). All other untoward medical occurrences observed during the screening period, including exacerbation or changes in medical history are to be captured on the medical history CRF/eCRF. See Section 7 Adverse Events and Toxicity Management for additional details.

6.3. Baseline Visit

The Baseline Visit should occur within 30 (\pm 3) days of the initial Screening Visit. All baseline tests and procedures should be completed prior to the receipt of the first dose of Tenofovir DF. Subjects will be dispensed Tenofovir DF medication at their Baseline Visit. Tenofovir DF should be initiated within 24 hours of the Baseline Visit.

6.3.1. Assignment

Once eligibility has been confirmed, subjects will be assigned a subject number and monitoring group.

6.3.2. Baseline Assessments

The following assessments and procedures will be performed and recorded on CRFs for Groups 1 and 2 at the Baseline Visit and prior to the subject's first dose of Tenofovir DF:

- Changes in medical status since screening
- Physical exam including body weight and height
- Blood samples for:
 - HBV DNA and HBV genotyping (A-H)
 - HBV serology (HBeAg and HBsAg; anti-HBe and anti-HBs (if Ag negative))

- HCV, HDV, HIV testing
- Hematology (CBC with differential and platelets,PT/INR)
- Serum renal chemistry (glucose, creatinine, creatinine clearance (calculated) , magnesium, bicarbonate, chloride, potassium, sodium), fasting required
- Liver chemistry tests (ALT, ALP, AST, total and direct bilirubin, total protein, albumin, GGT, LDH, CK), fasting required
- Serum bone chemistry (calcium, phosphorus, 1,25 hydroxy vitamin D, PTH, osteocalcin, bone alkaline phosphatase, N and C telopeptides), fasting required
- Urinalysis (glucose, protein, creatinine, phosphate, bicarbonate, blood, calcium), fasting required
- DEXA scan of spine and whole body (DEXA may be performed between Screening and Baseline Visits, but must be performed no later than the Baseline Visit), and prior to receipt of Tenofovir DF.
- Review of bone and renal AEs and any associated medical management
- Concomitant medications (including dietary supplements such as calcium, vitamin D, phosphorus)
- Tenofovir DF dispensing and instructions on appropriate dosing and administration
- Screening for pregnancy (urine screen)

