4. SUBJECT POPULATION

4.1. Number of Subjects and Subject Selection

100 subjects to receive treatment with Tenofovir DF and assigned to one of two monitoring groups (50 in each group). The subjects will be assigned to one of two monitoring groups using a validated computer-generated tool for randomization. Subjects will be assigned to Group 1 or 2 upon enrollment into the study but prior to Baseline laboratory and DEXA imaging assessments.

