5. ADMINISTRATION OF TENOFOVIR DF TREATMENT

5.1. Randomization, Blinding and Treatment Codes

After screening and once eligibility has been confirmed, subjects will be assigned a subject number and monitoring arm (i.e., Group 1 or Group 2). A centralized procedure will be used, to assign subjects to the respective monitoring arm. For the 96 weeks of the study, Tenofovir DF will be dispensed to the subject in numbered bottles from supplies stored at the study site. Tenofovir DF monitoring groups will be randomly allocated, but the allocation to one or the other group will not be blinded. Subjects will be informed of the two monitoring groups at the time of study screening and informed of their assignment to one of the two selected CHB management monitoring groups after consent is obtained at the subject's screening appointment.

All Baseline tests and procedures must be completed prior to the administration of the first dose of Tenofovir DF. Initiation of treatment with Tenofovir DF should take place within 24 hours of the Baseline Visit.

For duration of the study, Tenofovir DF 300mg will be supplied by Gilead.

5.1.1. Procedures for Breaking Treatment Codes:

Not applicable

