5.2.2. Packaging and Labeling

Tenofovir DF is packaged in white, high-density polyethylene (HDPE) bottles with a white child resistant cap. There are 30 tablets per bottle. Each bottle also contains silica gel as a desiccant to protect the product from humidity and fiber packing to protect the product during handling and shipping.

During Weeks 0 to 96, subjects will be provided with sufficient supplies for 12 weeks of dosing. At a minimum, each bottle will be labeled with a lot number, the protocol number, administration instructions, storage instructions, expiration date, Sponsor name and address. Additional information will be included according to the requirements of the protocol and local law.

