Female subjects of childbearing potential must agree to use protocol specified method(s) of contraception from the screening/enrollment visit throughout the study period and for 30 days following the last dose of Tenofovir DF or choose continuous heterosexual abstinence as a lifestyle choice. The investigator should counsel subjects on the protocol specified method(s) for avoiding pregnancy during the study. These methods are recommended due to the low failure rate (ie, less than 1% per year). See [Appendix Table 1](#) for the protocol specified contraceptive methods. Protocol specified contraceptive methods are as follows: (1) a combination of one hormonal method and one barrier method; (2) two barrier methods where one method is the male condom; or (3) use of an intrauterine device (IUD) or tubal sterilization; see below. Acceptable hormonal methods include injectable progesterone, progesterone implants, combination oral contraceptives, transdermal contraceptive patch, and vaginal ring. Acceptable barrier methods include diaphragm with spermicide, cervical cap with spermicide, and the male condom. Female subjects must use either a hormonal method or a barrier method if the partner has a vasectomy. If a subject has undergone tubal sterilization or has had a Copper T 380A IUD or LNG 20 IUD inserted, no other contraception is needed.

Complete abstinence from intercourse. Abstinence is an acceptable method of contraception only when it is in line with the subject’s preferred and usual lifestyle. Periodic abstinence (e.g., calendar, ovulation, symptothermal, post-ovulation methods) and withdrawal are not acceptable methods of contraception.

Female study subjects who are not heterosexually active must have periodic confirmation of continued abstinence from heterosexual intercourse and regular pregnancy testing while taking Tenofovir DF. The investigator should counsel subjects on the protocol specified method(s) for avoiding pregnancy in case the subject chooses to engage in heterosexual intercourse.

Female subjects of childbearing potential must have a negative serum pregnancy test at screening and a negative urine pregnancy test at baseline (Day 1) prior to receiving the first dose of Tenofovir DF. Lactating females must discontinue nursing before Tenofovir DF administration.

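### Minor, patient safety only: HIV, HCV and HDV are first tested at the visit where drug is dispensed, with no stated rule that results be known before the first dose

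*Protocol*

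**What the plan says.** **When the tests are done.** The Baseline list in Protocol 6.3.2 includes "HCV, HDV, HIV testing". The synopsis and Section 3.2 also name them as Baseline measures, by PCR. Protocol Appendix 2 has a single mark for this row, at Baseline. SAP Appendix 1 labels the row as screening but also marks it at Baseline only. The Screening list in 6.2.1 has chemistry, urinalysis, pregnancy testing and HBV serology, but none of these three tests, although that visit exists to settle eligibility: "Subjects will be screened within 30 days before assignment to determine eligibility for participation in the study".

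**When drug is given.** Section 6.3: "Subjects will be dispensed Tenofovir DF medication at their Baseline Visit. Tenofovir DF should be initiated within 24 hours of the Baseline Visit".

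**What must come before the first dose.** Section 5.1: "All Baseline tests and procedures must be completed prior to the administration of the first dose of Tenofovir DF". Section 6.3 repeats the rule in softer terms. For pregnancy, Appendix 5 names the result itself: females of childbearing potential need "a negative urine pregnancy test at baseline (Day 1) prior to receiving the first dose of Tenofovir DF".

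**What follows a positive result.** Nothing specific. Section 4.3 names no viral co-infection. Exclusion criterion 5 leaves unsuitable conditions to the investigator's opinion. The stopping lists in 3.5 and 6.6 do not name co-infection either.

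**When the group is assigned.** Section 4.1: "Subjects will be assigned to Group 1 or 2 upon enrollment into the study but prior to Baseline laboratory and DEXA imaging assessments". Section 6.3.1, which sits under the Baseline Visit heading, says: "Once eligibility has been confirmed, subjects will be assigned a subject number and monitoring group". SAP 3.8.2 instead places randomization after the baseline DXA scan, which conflicts with Section 4.1.

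**The concern.** The protocol orders three tests that bear on whether a subject should receive this treatment, but takes the sample at the visit where the drug is handed over. If a result comes back after the first dose, it cannot have informed the decision to start.

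This matters most for HIV. The study supplies tenofovir DF alone. Section 1.2.1 describes its HIV use as part of a combination, in a sentence that refers to adults. The paediatric HIV studies summarised in 1.2.3.1 and 1.4 also gave it with other antiretrovirals. Lamivudine, which appears in regimens described in both sections, is prohibited on study by 5.4.2, as is emtricitabine. A subject with unrecognised HIV could therefore start, and for a time continue, a regimen that differs from every HIV use the protocol describes, apart from a short lead-in in one study. For HCV and HDV the documents describe no comparable conflict. The gap there is only that nobody is told to look at the result and record a decision.

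**Working it through.** The documents give no figure on this point and no arithmetic applies. The check is of the order of events and the wording of the rules.

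1. **Could the result be known from Screening?** Not from a study test. Section 6.2.1 does not include the three assays, and both schedules mark them at Baseline only. Earlier clinical testing is neither required nor excluded, so *first tested* here means first tested within the study.

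2. **How long is there between sample and first dose?** Under 6.3, dispensing is at the Baseline Visit and dosing should start within 24 hours. No turnaround time is given, so it cannot be shown that the result would be late, or that it would be in time.

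3. **Does the rule on completed tests close the gap?** The rule in 5.1 could be read to mean that results are in hand. Two things count against that reading.
   - The Baseline list in 6.3.2 also contains HBV genotyping, HBV DNA, osteocalcin and N and C telopeptides. If *completed* meant *resulted*, all of these would have to be back before a dose due within 24 hours. That is unlikely to be the intent.
   - Where the protocol wants a result before dosing, it says so, as Appendix 5 does for pregnancy. It has no matching sentence for HIV, HCV or HDV.

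4. **Is there an instruction for a positive result?** Co-infection is missing from the exclusions in 4.3 and from the stopping lists in 3.5 and 6.6. Criterion 5 can deal with a co-infection already known. It cannot use a result that does not yet exist.

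5. **Why HIV in particular?** Section 5.3 gives tenofovir DF once daily and supplies no partner drug. Section 1.2.1 describes HIV use in combination. Section 5.4.2 bars antivirals active against HBV, naming lamivudine and emtricitabine. It does not bar every antiretroviral, but nothing in the plan would prompt one to be added for an infection not yet detected.

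A site that follows the text exactly can therefore start an undiagnosed HIV-positive adolescent on tenofovir DF alone. The documents show that this is possible. They do not show how often it would happen.

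**The case against.** The strongest reply is that the plan largely handles this. All Baseline tests must be completed before the first dose, and a completed test naturally has a result. Co-infection is not an exclusion, and the tests are listed beside HBV genotyping, so they may be meant to describe the population rather than to decide entry. Subjects are otherwise managed to local standards of care, and the investigator can stop drug later for toxicity, intercurrent illness or on request. No passage says that a short exposure harms an HIV-positive adolescent; one paediatric Phase 1 study in 1.2.3.1 used six days of tenofovir DF monotherapy before other drugs were added.

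Much of this stands. Characterisation is a legitimate purpose, later stopping is available, and no harm from a single dose or a few days is claimed. What does not stand is that the word *completed* settles the matter, for the two reasons given in the working. A test done only to characterise subjects can still return a finding that needs action, and no action is written down.

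Several stronger readings are tempting, and the documents do not support them:

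- *Assignment before the result is itself a hazard.* Both groups receive the same drug, formulation and frequency (3.3). A subject assigned but found positive before dosing need not be dosed, and would fall outside the SAP's Full Analysis and Safety sets, which require at least one dose. The documents also disagree on when assignment occurs. SAP 3.8.2 does not make it wait for viral results, because Section 6.3.2 allows the DEXA to precede the Baseline Visit.
- *The supply measures the exposure.* Section 5.2.2 says "During Weeks 0 to 96, subjects will be provided with sufficient supplies for 12 weeks of dosing". That is drug in hand, not time on monotherapy; the site can stop drug when a result arrives.
- *Testing at Screening gains a known amount of time.* The 30-day figure is a maximum. No minimum gap is set and no turnaround is stated, so the gain cannot be quantified.
- *HIV's absence from the ALT-flare reflex panel in 7.5.7.1 makes things worse.* That panel is conditional and post-dose, and has no bearing on what is known before dosing.

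**Conclusion.** The point holds as a minor patient-safety gap. HIV, HCV and HDV are first tested in the study at the dispensing visit, no text explicitly requires their results before the first dose, and no response to a positive result is stated. The schedule facts are firm. The consequence is a possibility: an undiagnosed HIV infection may be unknown when tenofovir DF is started without partner antiretrovirals.

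Its size cannot be given. It depends on the prevalence of unrecognised co-infection and on turnaround, and the documents state neither. The number affected may be zero. SAP 1.4 reports enrolment closed at 30, 15 per group.

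A reader might infer that co-infected subjects distort the BMD endpoint, the efficacy composite or the comparison of monitoring groups. The documents give no basis for that, and no such effect is claimed. Alpha, power and sample size are not involved.

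**What to change.** For a protocol of this design, move the HCV/HDV/HIV sample to the blood draw that already takes place at Screening, amending 6.2.1, 6.3.2 and Appendix 2, and add to 6.3:

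*HIV, HCV and HDV results must be available and reviewed by the investigator under exclusion criterion 5 before Tenofovir DF is dispensed; a subject found HIV positive is not started on study Tenofovir DF alone.*

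The added sentence does the protective work; moving the sample makes it practicable without delaying the Baseline Visit. Its second half in effect adds a condition on starting treatment, so the sponsor should adopt it deliberately.

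The cost is wording in those places, a laboratory-kit change, and testing some subjects who then fail screening.

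In this study, with enrolment closed, the only step left is optional: add baseline HIV, HCV and HDV status as a row in SAP Table 4. SAP 5.2 does not list it, and no planned table or listing title names it. The row would show whether anyone was affected, at the price of one line of reporting.

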6.4. Treatment Assessments

Unless fasting is required (i.e., serum renal chemistry and urinalysis, serum bone chemistry, liver chemistry) for the study visit, subjects should take their dose of Tenofovir DF prior to the visit with food.

6.4.1. Group 1: Week 4 Assessments

The following evaluations will be performed at Week 4 unless otherwise specified. Study visits are to be completed ± 7 days of the protocol-specified visit date, based on the Baseline Visit. Week 4 assessments are outlined in the following section (Section 6.4.4). Group 2 subjects will follow local standard of care for renal monitoring and AE collection.

The following assessments and procedures will be performed and recorded on CRFs:

- Changes in medical status or symptoms from prior visit

- Body weight and height
- Blood samples for:
 - Serum renal chemistry (creatinine, glucose, creatinine clearance (calculated), magnesium, bicarbonate, chloride, potassium, sodium), fasting required
- Urinalysis (protein, glucose, creatinine, phosphate, bicarbonate, blood, calcium) , fasting required
- Assessment of medication adherence
- Review of bone and renal AEs and any associated medical management
- Tenofovir DF dispensing and instructions on appropriate dosing and administration
- Concomitant medications (including dietary supplements such as calcium, vitamin D, phosphorus)

6.4.2. Group 1: Week 12 and 36 Assessments

Study Visit for Weeks 12 and 36 should be completed \pm 7 days of the protocol-specified visit date, based on the Baseline Visit. Group 2 subjects will follow local standard of care for renal monitoring and AE collection. The following assessments and procedures will be performed and recorded on CRFs:

- Complete physical examination including, vital signs, body weight and height
- Group 1: Urinalysis (protein, glucose, creatinine, phosphate, bicarbonate, blood, calcium), fasting required
- Blood samples for:
 - Group 1: Serum renal chemistry (creatinine, glucose, creatinine clearance (calculated), magnesium, bicarbonate, chloride, potassium, sodium), fasting required
 - Plasma HBV DNA (PCR method)
- Review of bone and renal AEs and any associated medical management
- Concomitant medications (including dietary supplements such as calcium, vitamin D, phosphorus)
- Assessment of medication adherence
- Tenofovir DF dispensing and instructions on appropriate dosing and administration

- Screening for pregnancy (urine screen)

Subjects who discontinue the study prior to the Week 12 or 36 Visit will complete all Week 12 or 36 assessments and procedures at an Early Drug Discontinuation Visit, to be completed within 72 hours of last dose of Tenofovir DF. Subjects who have received at least one dose of Tenofovir DF and permanently discontinue treatment will be followed for 24 weeks off treatment or up to initiation of an alternative treatment regimen, whichever occurs first.

